Feeding in neonates involves a sequence of sucking, swallowing, and breathing that requires coordination of the face, head, and neck muscles with the myelinated vagal regulation of the bronchi and the heart (11). In preterm neonates, the muscles needed to feed are underdeveloped, resulting in the need for OT rehabilitation to 'learn' feeding patterns. Preterm neonates' inability to feed effectively is the primary reason for prolonged hospital stays (12). In neonates with HIE, development of cortex and basal ganglia is interrupted, and depending on the severity, normal developmental plasticity is hindered, further contributing to their inability to feed (13). Both types of feeding difficulties involve complex motor learning, which requires integration of sensory and motor pathways. Treating oromotor difficulties during the learned task of feeding with noninvasive brain stimulation that promotes plasticity, poses a highly novel application of taVNS. Our major premise is that in babies at high risk for motor problems, simultaneously delivered brain stimulation via taVNS will boost motor cortical plasticity involved in a learned feeding task, leading to better feeding.

This protocol has 2 specific aims that will be investigated:

Specific Aim 1: Improved Motor Learning - We aim to investigate whether pairing taVNS with rehabilitation training of feeding behavior in preterm and HIE neonates will enhance and accelerate the learning of effective feeding behavior in a dose responsive manner. We call this treatment "taVNS-paired feeding." The primary outcome measures of taVNS-paired feeding will be daily oral milk feeding volume changes from before to during treatment, and number of infants reaching full oral feeds

between once and twice daily taVNS-paired feeding, duration to full feeds, as well as general motor functional impairment as measured by [name] Test of Early infant motor Performance (STEP). Our hypothesis is that taVNS-paired feeding for preterm neonates is feasible, safe and effective at reducing length of stay solely for feeding reasons, compared to historical controls. As part of our safety investigations with separate funding, we may perform taVNS during a clinical modified barium swallow study with pediatric speech language pathologists performing the study and compare 10 swallows with stimulation on and off to determine if taVNS affects swallowing parameters.

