Up to 40 preterm/HIE neonates will be enrolled in this prospective, open-label safety and feasibility trial, with a dose response. The experimental paradigm consists of 2 to 3 weeks of once or twice daily taVNS-paired feeding.

Our control group was investigated by Drs. [name] and [name] at MUSC, who have researched all infants failing feeding and getting Gastrostomy tubes in our nurseries over the past 5 years. We can compare our data to this historical group at our own institution.

All consented participants will receive the active stimulation condition.

taVNS Stimulation (in Detail)

After obtaining consent and describing this procedure to the parents and all members of the baby's care team, we will first, with a 500 μ s, 25Hz pulse, gradually increase the intensity of the TENS unit until the baby can first feel something in their ear. We will use the facial expression change and fidgety movements to determine when the infants feel the stimulation. This intensity will be recorded as the perceptual sensory threshold. The stimulation intensity we will use for this study on taVNS-paired feeding is a small decrement from the perceptual sensory threshold for each infant (-0.1mA), a point at which they should not react to the stimulation. We will retest the sensory threshold before every session.

Determination of Perceptual Threshold

1. Electrode clip will be placed on the left tragus in an enrolled infant at rest. Starting at 0.2mA at 25Hz, we will deliver 5 seconds of pulses, and increase by 0.1mA until the perceptual threshold is achieved by observation of the infant's facial expression, fidgety movements, or NIPPS score. This will be termed the perceptual threshold.
2. We will then deliver this level of microcurrent while the infant is feeding on the first day to determine if the perceptual threshold changes with feeding. Current will then be held constant while pulse width and frequency will be set at 500us and 25Hz, respectively.

3. Finally, we will decrease the microcurrent by 0.1mA *below the perceptual threshold* and administer this taVNS treatment during the feeding and deliver this only while the infant is actively sucking from the bottle.
4. The total duration of this 'on-and-off' taVNS stimulation treatment will continue for 30 minutes or the duration of the feed.
5. We may manually trigger the taVNS stimulation or place a gel EMG electrode over the temporomandibular joint area to trigger the taVNS impulse.

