Once the daily taVNS intensity has been determined, the treatment will continue to be administered in conjunction with the daily OT feeding once or twice daily.

As the baby begins to suck from the bottle or breast, stimulation will be triggered and a timer will be started. Sometimes the infant has non-nutritive sucking and it is difficult for the operator to discern between these lip motions and real suck/swallow. We wish to stimulate during sucking motions that include swallowing but may occasionally pair with ineffective and incomplete lip sucking, characteristic of more immature patterns. We may use manual triggering by a research assistant or triggering by the EMG at the buccinator muscle to ensure accurate delivery of impulses and pairing of impulse with sucking/swallowing.

The stimulation will continue until the baby stops sucking, at which point the stimulation will be stopped and the timer will stop, until the baby begins to suck again. The typical feeding OT session lasts up to 30 minutes. Physiological data will be monitored continuously as measured by the echocardiogram (ECG). Neonatal Infant Pain Scale (NIPS) data will be collected at beginning, middle and the end of treatment session. The NIPS rating scale currently in use in the nursery is included in this submission. These studies will be conducted in both level II and III Neonatal Intensive Care Units (NICUs), depending on the location and of the enrolled participants.

taVNS Device

taVNS will be delivered to the left ear only using an active (tragus) location for the taVNS clip using either the Digitimer Type DS7AH (Digitimer Ltd, Hertfordshire, England) or Soterix 0125-LTE stimulator customized for our infant trials. Both are TENS units and are cleared by the FDA for electrical nerve stimulation in research trials (See uploaded documents from Soterix). We also recently received FDA Breakthrough device designation for our BabySTrong taVNS infant feeding system, based on a customized 0125-LTE Soterix taVNS unit. TENS units are widely used in children with overactive bladder and dysfunctional voiding and stooling (44-45) and for analgesia in children, and as a treatment for chronic pain, including cancer (46). A custom electrode, embedded within a carbon matrix will be used to stimulate the auricular branch of the vagal nerve at the tragus. We will then trigger the taVNS unit to deliver the microcurrent or to stop the microcurrent when the infant is actively sucking and swallowing.

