For safety we will compare HR changes from baseline to during taVNS within subjects. We will compare treatment before and after the taVNS-paired feeding treatment for the rate of feeding volume increase, and days to full po feeds. We will use repeated measures ANOVA to analyze repeated measures such as HR over 5 minutes and mean daily feeding volumes in 7-10 day epochs. We will analyze the number of infants who reach full feeds vs requiring G-tube during taVNS-paired feeding, between once and twice daily stimulation by Chi-squared. We will assess differences in kurtosis parameters from pre-to post taVNS scans by paired t-test, and between those that reach full oral feeds vs those that require a Gtube by unpaired t-test.

Estimated Difficulties, Limitations and Time Frames

Estimated Difficulties. Many of the initial parameters for taVNS in humans, such as frequency and pulse width, were accomplished in trials at MUSC by [name] et al. that were approved by the IRB. In one sense, we will be shrinking many of the components into miniature form to deliver stimulation to neonates and infants. In spite of the clear differences in size and skin between the neonatal and adult ear, the custom electrodes have been fitted to several different weights of infants (2.5-4.0 kg).

Limitations. We will not be delivering a SHAM stimulation paradigm (electrodes and Digitizer with appearance of taVNs treatment without actual current). Our goal is to determine safety and feasibility of active treatment with a dose response in order to investigate whether this should be administered in a larger randomized control trial. In this respect, the comparison we lose in not having a SHAM stimulation is offset by the validation we will receive in the safety and feasibility of active treatment. We will compare our overall results with characteristics of infants who required a Gtube from [name] and [name]'s publications.

Estimated Time Frames. The duration of the study will likely be ~4 years, with 2 years of active enrollment and 18 months of follow-up.

E. PROTECTION OF HUMAN SUBJECTS

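### Aim 1's before-to-during daily volume counts the stimulated feeds, so on its own it cannot separate a momentary effect from learning

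*Combined protocol and SAP*

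**What the plan says.** Section A, Specific Aim 1 is framed as motor learning: it asks whether taVNS-paired feeding "will enhance and accelerate the learning of effective feeding behavior in a dose responsive manner". Volume comes first among its measures: "The primary outcome measures of taVNS-paired feeding will be daily oral milk feeding volume changes from before to during treatment". The same sentence goes on to the number of infants reaching full oral feeds under once and twice daily treatment, duration to full feeds, and STEP. The hypotheses that close Section B treat a larger milk intake as the visible sign of faster learning.

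Section D, Data Analysis, applies repeated measures ANOVA to "mean daily feeding volumes in 7-10 day epochs". It also says: "We will compare treatment before and after the taVNS-paired feeding treatment for the rate of feeding volume increase, and days to full po feeds". The period after treatment is not defined there, and Aim 1 speaks of the treatment period itself. The only comparison by frequency that Data Analysis names is a chi-squared test of full feeds versus G-tube.

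On delivery, Study Design states: "The experimental paradigm consists of 2 to 3 weeks of once or twice daily taVNS-paired feeding". Treatment is given "in conjunction with the daily OT feeding once or twice daily", and step 3 of the perceptual-threshold procedure is to "deliver this only while the infant is actively sucking from the bottle". Trained research staff attend every session (Safety Monitoring). All infants are stimulated, and there is no sham (Study Design; Limitations).

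No section separates stimulated from unstimulated feeds or defines a feeding-volume window with stimulation off.

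**The concern.** If an infant has learned to feed better, the gain should show at feeds given without stimulation. Aim 1 does not spell this out; it is the ordinary meaning of learning a skill. A daily volume adds the stimulated feeds to the rest. Because current is on while the infant sucks, any immediate effect of the current, or of the research attendance, acts on the very milk that is counted.

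The protocol itself leaves an immediate effect open: Aim 1 describes an optional, separately funded swallow study with stimulation on and off. No sham or concurrent unstimulated group is available to subtract such an effect.

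The results are meant to inform whether a larger randomised trial should follow. A volume gain credited to plasticity could in fact be confined to the treated feeds. The same gain, set out by frequency, could be taken as a dose response.

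**Working it through.** The plan gives no power, alpha, effect size or SD and does not derive the 40 infants, so there is no stated figure to reproduce. The check is an accounting model with learning set to zero.

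**Inputs from the protocol**
- Stimulated feeds per day, k = 1 or 2 (Study Design).
- Up to 40 infants (Study Design).
- Session duration raised gradually over the first sessions (Section B); the length of the ramp is not given.

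**Assumptions, none in the protocol**
- Feeds per day, F = 8 (range 6 to 12).
- Share of each feed taken by mouth at baseline, b = 50% or 70%.
- Momentary gain at a stimulated feed, m = 20 or 50 points of a feed, at most 100% − b.
- SD of change 5, 10 or 15 points of full daily volume; two-sided 0.05; an equal 20/20 split by frequency.

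**Step 1: level.** Daily oral share = b + (k/F) × m, so the before-to-during change is (k/F) × m, while the change at unstimulated feeds is 0.
- F = 8, m = 20: 1/8 × 20 = 2.5 points once daily; 2/8 × 20 = 5.0 points twice daily.
- Ceiling, with stimulated feeds taken wholly by mouth and b = 50%: 6.25 and 12.5 points at F = 8; 8.3 and 16.7 at F = 6; 4.2 and 8.3 at F = 12.
- In millilitres the rise is d versus 2d. For an assumed d of 10 to 20 mL it is 10 to 20 versus 20 to 40 mL/day.

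**Step 2: would it show?** These are normal approximations, illustrative only. At m = 20 the mean rise over both frequencies is (2.5 + 5.0)/2 = 3.75 points, and the twice-minus-once difference is 2.5.
- Before-to-during, n = 40, SD 10: SE = 10/√40 = 1.58; 3.75/1.58 − 1.96 = 0.41; probability 0.66.
- Twice versus once, 20 per group, SD 10: SE = 10 × √(2/20) = 3.16; 2.5/3.16 − 1.96 = −1.17; probability 0.12.

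| Probability of a significant result with zero learning | SD 5 | SD 10 | SD 15 |
|---|---|---|---|
| Before-to-during, m = 20 | 0.997 | 0.66 | 0.35 |
| Before-to-during, m = 50 | 1.00 | 1.00 | 0.98 |
| Twice versus once, m = 20 | 0.35 | 0.12 | 0.08 |
| Twice versus once, m = 50 | 0.98 | 0.51 | 0.26 |

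**Step 3: the other outcomes.**
- Full feeds: even at the ceiling with F = 8, the day's oral share reaches only 56% (once) or 63% (twice) from b = 50%, and 74% or 78% from b = 70%. A momentary effect could tip only infants already close to full feeds, which the plan does not define.
- Rate of increase: with slopes fitted within each period (10 days before, 14 during), a constant momentary gain changes the slope by 0. A 5-day ramp-in at m = 20 gives about 0.12 and 0.24 points per day.

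**The case against.** The strongest reply is that Aim 1 does not rest on volume level alone. Full oral feeding requires success at the unstimulated feeds too, so it largely captures carry-over, and step 3 supports this. STEP is compared with baseline after treatment, and imaging is done before and after the two-week course. A reader might infer that the trial as a whole cannot tell learning from an acute effect, or that nothing is measured after the course. The documents do not support either; what is missing is a post-course feeding-volume window.

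A reader might also infer that the planned dose-response result is biased upward by construction. The named frequency test is on full feeds versus G-tube, which a gain at one or two feeds a day cannot produce alone. Only a once-versus-twice comparison of volume would carry the artefact, and neither Aim 1 nor Data Analysis clearly specifies one. It remains a natural reading of the data, given that Aim 1 asks about dose response and Section E.3 calls this a dose-finding study.

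Two further replies stand. Section A says OT usually works with infants once a day, so an OT-led feed is normally part of the days before treatment; what is new is stimulation and research attendance. And this is an open-label pilot whose benefit hypotheses rank behind safety and feasibility (Section B), which limits the weight of the point. None of this makes the volume level interpretable as learning.

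**Conclusion.** The point holds for one primary measure. The before-to-during level of daily oral volume cannot by itself separate a momentary effect at the stimulated feeds from learning that carries over. Any comparison of that level by frequency would show d versus 2d with no carry-over, provided the gain per stimulated feed is equal. A false before-to-during signal is plausible at moderate effects (0.66 at m = 20, SD 10). A false dose signal in volume needs a large momentary effect or a small SD.

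That stimulated feeds are counted is the natural reading of a daily volume, not explicit text. Feeds per day, baseline share, momentary gain, SD, alpha and the equal split are all assumed. The full-feeds test, days to full feeds, rate of increase and STEP are much less affected. This is an inexpensive improvement to an outcome definition, not a flaw that undermines the trial.

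**What to change.** In Specific Aim 1 and Data Analysis:

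1. Flag each feed as stimulated or not.
2. Report mean oral volume per scheduled feed at unstimulated feeds on treatment days, against comparable feeds (not OT-led) before treatment. The match matters because the OT-led feed is normally the one that becomes stimulated.
3. Show stimulated-feed volume separately.
4. Base any learning or dose statement drawn from volume on the unstimulated-feed result.
5. Reconcile the before-to-during wording of Aim 1 with the before-and-after wording of Data Analysis, and define both periods.
6. Treat any volume window after the course as supportive only: discharge and G-tube placement make the infants still in hospital a selected group.

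The cost is wording and one yes/no field per feed, assuming that volumes are charted feed by feed. One or two feeds a day leave the learning measure, and the estimate may be smaller. Without a concurrent control, the contrast still does not separate taVNS from maturation or ongoing OT, and the report should say so.

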**Medical University of South Carolina
Protocol**

PI Name: [name]

Co-PI: [name]

Study Title: Noninvasive Brain Stimulation to Improve Oromotor Function In Neonates

Once protocol is complete, save it as a Word document. Go back to the IRB application and upload the protocol.

TABLE OF CONTENTS – *Prepare a table of contents based on the following outline, including page numbers, and insert here.*

Specific Aims.....	2
Background and Significance.....	2
Preliminary Studies.....	3
Research Design and Study Methods.....	4
Protection of Human Subjects.....	8
References.....	15
Facilities.....	18

A. SPECIFIC AIMS

Preterm infants and term infants who suffer hypoxic ischemic encephalopathy (HIE) are at high risk for motor problems, which primarily manifest as feeding delays during their neonatal hospital admission. Oromotor dyscoordination is very common in both groups of infants, and typically takes 3-6 weeks of working on oral feedings in the hospital before the infant may take enough breast milk or formula to sustain adequate growth for discharge. Occupational therapy usually works with infants once a day to ensure that the feeding particulars, such as nipple choice, frequency of oral feeding, do not tax infant physiology too greatly and to guide learning this motor skill. Feeding difficulty is the primary reason for delayed discharge of preterm or HIE infants. Many of these infants will not be able to master this motor skill before term age (40-42 weeks gestation) and will receive a gastrostomy tube (G-tube) for direct gastric feeding, in order that they may finally be discharged from the hospital to home. Over the past 5 years in our MUSC NICU (2012-2016), we have placed an average of 40 G-tubes per year. This procedure requires general anesthesia for both insertion and eventual take down, and leaves scars in the epigastric area. The G-tube also reinforces the parental perception that their child is not normal and that he or she has a more limited developmental potential than a 'normal' child.

Even with significant brain injury, we know that neuroplasticity in infants may lead to improved, and even near normal outcomes. This neuroplasticity involves stimulating neurogenesis and reparative inter-neuronal connections to improve motor skills in neonatal animal models and in adults after stroke. In addition, we know that rehabilitative training may be enhanced by brain stimulation using a variety of modalities.

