[name], Ph.D, obtained his doctorate under [name], and has extensive experience and background in clinical TMS and taVNS, especially in the development of novel protocols for neurological disorders. His thesis work involves systematic elucidation of the dose response of taVNS on heart rate, use of heart rate as a biomarker of taVNS effect, and the use of taVNS with fMRI in determining pathways and regions affected by taVNS in adults. He determined that the 'on' pulse heart rate change was a mean of -3 beats per minute (bpm) while the 'off' pulse heart rate change was +6 bpm. Although these are statistically significant and measurable changes, they are physiologically insignificant. Nevertheless, this will be an important biomarker for infants, but is not expected to result in safety concerns. [name] careful and thorough studies lay the safety and efficacy groundwork for the current proposal.

D. RESEARCH DESIGN AND METHODS (including data analysis)

Due to the novelty of these studies, [name] will be present for each taVNS-paired feeding session conducted in the first participants, and as needed thereafter. [name] and or [name] will monitor taVNS effects. If any adverse events are noticed which are not described in the consent or are serious, we will inform the IRB before continuing with the next enrolled subject. Importantly, all of these methods have been done before, and published by our and other groups in adults, and we believe these extra precautions will assure the safety and well-being of any participants enrolled.

taVNS-paired feeding to enhance feeding behavior in neonates

Screening

Prospective participants will be identified by the PI ([name]) at the MUSC neonatal intensive care units (Level II and III), and checked for potential inclusion (please see the uploaded taVNS screening form). [name], and other clinical OTs based in the nursery may also mention the study to parents and refer them to [name] if they are interested in participating.

Participants

Inclusion criteria:

Infants must be clinically stable, on minimal respiratory support (nasal cannula, or room air), in discussions about Gtube placement for poor po feeding and are currently greater than or equal to 39 weeks post-menstrual age and

- 1) If born premature have been working on oral feeding for 30days;
or

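### Effectiveness is stated as shorter stay, which no outcome or analysis measures and which counts a G-tube discharge as a completed stay; days to full feeds has no rule for G-tube infants

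*Combined protocol and SAP*

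**What the plan says.** Section A, Specific Aim 1, puts the effectiveness hypothesis as a treatment "effective at reducing length of stay solely for feeding reasons, compared to historical controls". The outcomes listed just before it are "daily oral milk feeding volume changes from before to during treatment, and number of infants reaching full oral feeds", the latter compared "between once and twice daily taVNS-paired feeding, duration to full feeds, as well as general motor functional impairment". That makes four: change in oral volume, number reaching full feeds, duration to full feeds, and the STEP motor score. Length of stay is not one of them.

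The opening of Section A explains that infants who do not master feeding get a G-tube "in order that they may finally be discharged from the hospital to home". Under Participants (Section D), entrants must already be "in discussions about Gtube placement for poor po feeding". Study Design adds: "The experimental paradigm consists of 2 to 3 weeks of once or twice daily taVNS-paired feeding". It names as controls a group drawn from investigators "who have researched all infants failing feeding and getting Gastrostomy tubes in our nurseries over the past 5 years".

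Data Analysis sets up a before-and-after comparison "for the rate of feeding volume increase, and days to full po feeds". Separately, it compares full feeds against G-tube, once versus twice daily, by Chi-squared. It contains no analysis of stay. The Limitations paragraph promises a comparison with the historical infants' characteristics but does not say which.

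**The concern.** There are two linked gaps.

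First, the effectiveness hypothesis has no matching outcome or analysis, and the measure it names treats a G-tube differently from the rest of the plan. For stay, a G-tube is an exit from hospital and closes the count of days. For the Chi-squared comparison, the same event is a failure. Because the historical group was selected for having had a G-tube, every control left by that route. The sign of a stay comparison then depends on how soon G-tubes were placed in each group as well as on whether infants learned to feed.

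Second, days to full oral feeds has no stated handling for infants who get a G-tube. Without a rule, only infants who succeed contribute a value, and the summary can look favourable however few they are.

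At stake is the decision that the Limitations paragraph says this study should inform, namely whether a larger randomised trial is warranted. Stay could fall because G-tubes came sooner, or rise while many infants were spared one.

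**Working it through.** The plan gives no figure for stay, time to G-tube or response rate, so there is nothing to reproduce. The check asks in which direction mean stay moves.

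**Inputs**
- C, course length: 14 or 21 days (Study Design, 2 to 3 weeks).
- w, days from entry to G-tube discharge without taVNS: not given; assumed 7 to 28.
- Ts, days from entry to discharge in infants who reach full feeds: not given; assumed 10.
- p, share reaching full feeds: not given; assumed 50%.

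**Formulas.** Comparison infants all leave by G-tube at w, as the historical group did. Mean treated stay = p × Ts + (1 − p) × F, where F is the stay of infants who fail:
- G-tube planning follows the course: F = C + w.
- G-tube planning runs in parallel: F = max(C, w).

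For C = 14, w = 14:
- Following: 0.5 × 10 + 0.5 × 28 = 19.0; change 19.0 − 14 = **+5.0 days**.
- Parallel: 0.5 × 10 + 0.5 × 14 = 12.0; change 12.0 − 14 = **−2.0 days**.

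| C | w | Treated stay, following | Change | Treated stay, parallel | Change |
|---|---|---|---|---|---|
| 14 | 7 | 15.5 | +8.5 | 12.0 | +5.0 |
| 14 | 14 | 19.0 | +5.0 | 12.0 | −2.0 |
| 14 | 21 | 22.5 | +1.5 | 15.5 | −5.5 |
| 14 | 28 | 26.0 | −2.0 | 19.0 | −9.0 |
| 21 | 14 | 22.5 | +8.5 | 15.5 | +1.5 |

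Half the infants avoid a G-tube in every row, yet the sign varies.

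**Break-even when planning follows the course.** Stay falls only if p > C / (C + w − Ts). With C = 14 and Ts = 10: w = 14 gives 14/18 = 78%; w = 21 gives 14/25 = 56%; w = 7 gives 14/11, above 1, so stay falls at no p.

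**Second check, constant daily hazards (all assumed).** Let a be the hazard of full feeds and g the hazard of G-tube discharge. Mean stay = 1/(a + g); share reaching full feeds = a/(a + g).
- Untreated, a = 0.01, g = 0.06: 1/0.07 = 14.3 days; 14% reach full feeds.
- Treated, a = 0.03, g = 0.02: 1/0.05 = 20.0 days; 60%.
- Treated, a = 0.03, g = 0.06: 1/0.09 = 11.1 days; 33%.

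The last two lines share the same feeding hazard. Earlier G-tubes alone shorten stay from 20.0 to 11.1 days while the share reaching full feeds falls from 60% to 33%.

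**Days to full feeds.** With the planned maximum of 40 infants and the same assumed 50%, 40 × 0.5 = 20 would have a value. The other 20, if they get a G-tube, would have none under the current text.

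**The case against.** The plan is not blind to G-tube failure. Duration to full feeds is one of four listed outcomes, and the Chi-squared comparison already scores a G-tube as failure, so an effect on the number fed orally would be visible there. Section B ranks efficacy below safety and feasibility, and Section E.3 says G-tube avoidance cannot be determined from this study. This stands and limits the consequence.

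A reader might infer that an effective treatment will appear to lengthen stay. The documents do not support that. A rise requires G-tube discharge to be deferred, or full feeding to take longer than the usual wait for a G-tube, and neither time is given. Infants enter with a G-tube already under discussion, so planning could run in parallel. Where stay does lengthen, the lengthening is real: it is a true cost of a two- to three-week course, and a reason to keep reporting stay.

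A reader might also infer that the problem holds whichever control group is used. It does not. If concurrent controls waited through the same 14 days, all failed and left at 14 + 14 = 28 days, the treated mean of 19.0 would be 9.0 days shorter. The reversal needs controls who skip the course and leave by G-tube.

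Nor can full feeding simply replace stay in the historical comparison. Controls chosen for having had a G-tube have zero or near-zero incidence of full feeds by selection, and they have no first taVNS session as a time origin.

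Finally, it would go too far to say that a G-tube infant never reaches full feeds. The protocol does not say whether oral feeding achieved after discharge would count.

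**Conclusion.** The point holds in a limited form. The stated effectiveness hypothesis has no corresponding outcome or analysis, and pooled stay against a G-tube-only group cannot be read as evidence for or against better feeding. The size is illustrative only: +5.0 or −2.0 days for the same 50% success rate, according to whether G-tube planning follows or accompanies the course. It rests on assumed p, w and Ts; only the course length is documented. The missing rule for G-tube infants in days to full feeds does not depend on those assumptions. In a safety and feasibility pilot this should be corrected, but it does not undermine the study's main purpose.

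**What to change.** - **Data Analysis:** estimate time from first taVNS session to full oral feeds within the treated cohort, overall and by once or twice daily dosing, as a cumulative incidence with G-tube as a competing event. State whether full oral feeding after a G-tube discharge counts.
- **Specific Aim 1:** align the effectiveness hypothesis with the feeding outcomes already listed.
- **Length of stay:** report it descriptively by exit route (full oral feeds or G-tube). Draw no effectiveness conclusion from pooled stay against the historical G-tube group, and do not compare full-feed incidence with that group.

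The cost is a wording change and one added analysis. It uses dates of first session, full feeds, G-tube and discharge, which the existing outcomes and the planned extraction of postnatal course and surgeries from the medical record should supply. Treatment and sample size are unchanged. The sponsor gives up the headline length-of-stay claim.
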